## 3.4.2. Subject Subgroups for Safety Analyses

- 1) Incidence of all treatment-emergent AEs (TEAEs) will be analyzed for the following subject subgroups (also see Section 7.1.6):
  - Age (years): (a)  $\leq 50$  and (b)  $\geq 50$
  - Sex: (a) male and (b) female
  - Race: (a) black and (b) nonblack
  - Region: (a) US and (b) Ex-US
- 2) Renal-related laboratory tests (ie, serum creatinine and eGFRCG) and fasting metabolic laboratory tests will be analyzed for each subgroup of baseline NRTI backbone: (a) F/TAF (b) F/TDF

- 3) Selected safety endpoints may be analyzed for the following subject subgroups for randomized phase analysis and for all B/F/TAF analyses (see Section 8.1 for details):
  - Subjects with HIV/HBV coinfection at baseline
  - Subjects with incident HIV/HBV coinfection while on study drug (if any)
- 4) Selected safety endpoints will be analyzed for the following subject subgroups for randomized phase analysis and for all B/F/TAF analyses (see Section 8.2 for details):
  - Subjects with HIV/HCV coinfection at baseline
  - Subjects with incident HIV/HCV coinfection while on study drug (if any)

# 3.5. Multiple Comparisons

The noninferiority evaluation of the proportion of subjects with HIV-1 RNA  $\geq$  50 copies/mL at Week 48 was the prespecified primary comparison. However, 1 interim IDMC analysis was performed prior to the analysis for the primary endpoint and an alpha penalty of 0.00001 was applied. Therefore, the alpha level for the primary endpoint (ie, the proportion of subjects with HIV-1 RNA  $\geq$  50 copies/mL at Week 48) was adjusted to 0.04999 (corresponding to 95.001% confidence interval [CI]) using both the FAS and the Week 48 PP analysis set. The alpha level for the key secondary efficacy endpoint, the proportion of subjects with HIV-1 RNA < 50 copies/mL at Week 48, will be also adjusted to 0.04999 (corresponding to 95.001% CI) to be conservative.

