#### 8.5.2. Secondary Analyses

The proportion of subjects with HIV-1 RNA < 50 copies/mL at Week 48 as defined by the US FDA-defined snapshot algorithm will also be summarized. The 95% CIs will be constructed in the same manner as described for the primary efficacy endpoint. However, non-inferiority will be assessed using a margin of 10%. It will be concluded that B/F/TAF FDC is noninferior to DTG+F/TAF if the lower bound of the 2-sided 95% CI of the difference between treatment groups (B/F/TAF group – DTG+F/TAF group) in the response rate is greater than -10%.

The change from baseline in CD4+ cell count at Week 48 will be summarized by treatment using descriptive statistics. The differences and the associated 95% CIs will be constructed using an Analysis of Variance (ANOVA) model, including treatment (B/F/TAF group vs. DTG+F/TAF group), prior NRTI use (F/TAF vs. F/TDF) and history of NRTI resistance as fixed effects in the model.

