## 1.3. Sample Size and Power

A total of approximately 520 HIV-1 infected subjects, randomized in a 1:1 ratio to 2 treatment groups (260 subjects per treatment group), achieves at least 90% power to detect a non-inferiority margin of 4% in difference in percentage of subjects with HIV-1 RNA ≥ 50 copies/mL at Week 48 between the 2 treatment groups.

For sample size and power computation, it is assumed that both treatment groups have 2% of subjects with HIV-1 RNA  $\geq 50$  copies/mL at Week 48 (based on the historical Gilead Genvoya® and Stribild® studies), that a non-inferiority margin is 4%, and that the significance level of the test is at a one-sided 0.025 level. Sample size and power calculations were made using the statistical software package nQuery Advisor (Version 6.0).

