## 6.1.1.4. Primary Analysis of the Primary Efficacy Endpoint

The analysis purpose of the primary efficacy endpoint is to assess the noninferiority of switching to B/F/TAF relative to DTG + F/TAF. Noninferiority will be assessed using a conventional 95% CI approach, with a noninferiority margin of 4%.

For the interim analysis performed for the IDMC at Week 12, an alpha of 0.00001 has been spent. Therefore, the significance level for the 2-sided test in the primary analysis at Week 48 will be 0.04999 (corresponding to 95.001% CI).

The point estimate of treatment difference (B/F/TAF group – DTG+F/TAF group) in the percentage of subjects with HIV-1 RNA  $\geq$  50 copies/mL and the associated 2-sided 95.001% CI will be constructed based on an unconditional exact method using 2 inverted 1-sided tests.

It will be concluded that B/F/TAF is noninferior to DTG+F/TAF if the upper bound of the 2-sided 95.001% CI of the difference between treatment groups (B/F/TAF group – DTG+F/TAF group) in the percentage of subjects with HIV-1 RNA  $\geq$  50 copies/mL is less than 4%.

The number and percentage of subjects with HIV-1 RNA < 50 copies/mL, HIV-1 RNA ≥ 50 copies/mL, and reasons for no virologic data at Week 48 will be summarized.

If noninferiority of B/F/TAF versus DTG+F/TAF is established, the same 95.001% CI used in evaluating noninferiority at Week 48 will be used to evaluate superiority. If the upper bound of the 95.001% CI is less than 0, then superiority of B/F/TAF over DTG+F/TAF is established. The 2-sided Fisher's exact test will also be used to assess superiority as a secondary assessment.

The FAS will be used for the primary efficacy endpoint analysis and the superiority evaluation.

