#### 6.1.2. Secondary Efficacy Endpoints

6.1.2.1. Definition of the Secondary Efficacy Endpoints

The secondary efficacy endpoints include:

- The proportion of subjects with HIV-1 RNA < 50 copies/mL at Week 48 as determined by the US FDA-defined snapshot algorithm
- The change from baseline in CD4+ cell count at Week 48

The analyses for the secondary efficacy endpoints will be conducted using the FAS and the Week 48 PP analysis set, respectively.

- 6.1.2.2. Analysis of the Secondary Efficacy Endpoints
- 6.1.2.2.1. Analysis of the Proportion of Subjects with HIV-1 RNA < 50 copies/mL as Determined by US FDA-defined Snapshot Algorithm

The proportion of subjects with HIV-1 RNA < 50 copies/mL at Week 48 will also be analyzed by the US FDA-defined snapshot algorithm based on the FAS and Week 48 PP analysis set, respectively.

Proportion of subjects with HIV-1 RNA < 50 copies/mL at Week 48 as determined by US FDA-defined snapshot algorithm will be analyzed similarly to the primary efficacy endpoint. However, the noninferiority margin used for the proportion of subjects with HIV-1 RNA < 50 copies/mL will be 10%.

Similarly to the primary efficacy endpoint, noninferiority will be assessed using the conventional CI approach. The point estimate of treatment difference (B/F/TAF group – DTG+F/TAF group) in the percentage of subjects with HIV-1 RNA < 50 copies/mL and the associated 2-sided 95.001% CI will be constructed based on an unconditional exact method using 2 inverted 1-sided tests.

It will be concluded that B/F/TAF is noninferior to DTG+F/TAF if the lower bound of the 2-sided 95.001% CI of the difference between treatment groups (B/F/TAF group – DTG+F/TAF group) in the percentage of subjects with HIV-1 RNA < 50 copies/mL is greater than –10%.

The above analysis will be performed using both the FAS and the Week 48 PP analysis set.

In addition, the following analyses will be performed using the FAS to evaluate the interaction between region and treatment to assess homogeneity of treatment effect across different regions.

A region is defined as multiple sites combined based on geographical locations (see Appendix 2 for region definition).

For each region, the difference in the proportion of subjects with HIV-1 RNA < 50 copies/mL between treatment groups and its 95% CI will be calculated based on an unconditional exact method using 2 inverted 1-sided tests.

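### The key secondary non-inferiority conclusion (10% margin) carries the full alpha with no condition on the primary, so error across the two claims is not controlled

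*SAP*

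**What the plan says.** SAP 3.5 states that the non-inferiority evaluation of HIV-1 RNA ≥ 50 copies/mL at Week 48 "was the prespecified primary comparison". Because of one IDMC analysis, "an alpha penalty of 0.00001 was applied", which leaves 0.04999 two-sided. The section then turns to the endpoint it calls key secondary, HIV-1 RNA < 50 copies/mL, whose alpha "will be also adjusted to 0.04999 (corresponding to 95.001% CI) to be conservative".

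SAP 6.1.2.2.1 gives that endpoint its own decision rule: "It will be concluded that B/F/TAF is noninferior to DTG+F/TAF if the lower bound of the" two-sided 95.001% interval for the difference is above −10%. The rule is applied to both the FAS and the Week 48 PP set. Protocol 8.5.2 says the proportion will also be summarized, then adds: "However, non-inferiority will be assessed using a margin of 10" percent, with the same form of conclusion.

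The one conditional step in the efficacy plan is in SAP 6.1.1.4, on superiority for the primary endpoint: "If noninferiority of B/F/TAF versus DTG+F/TAF is established, the same 95.001% CI" is used again. Neither document contains a testing order, a gate or an alpha split between the primary and the key secondary endpoint.

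**The concern.** Two non-inferiority conclusions in nearly the same words can be drawn from one trial, each at the full level. The only adjustment described is for the interim look, so calling the second level conservative does not address having a second claim.

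The wording goes beyond description. The endpoint is labelled key, has its own margin and adjusted alpha, and ends in a formal conclusion. The other secondary endpoint, change in CD4+ cell count, gets only an estimate and an interval.

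At stake is how a mixed result is read. If the primary missed its 4% margin, the plan as written would still allow a formal statement that B/F/TAF is non-inferior on the other endpoint, and nothing ranks the two statements. SAP 1.4 puts power for the primary at 85%, so a miss is a realistic outcome even with no true difference.

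**Working it through.** **Inputs from the documents.** Alpha 0.04999 two-sided for each endpoint (SAP 3.5). Margins 4% and 10% (SAP 6.1.1.4, 6.1.2.2.1). Failure rate 2% per arm and one-sided 0.025 at design (SAP 1.3). N = 565 and 85% power by the exact method (SAP 1.4).

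**Assumptions.** Split 283/282. Share of subjects without virologic data in the control arm 3% to 9%. The documents give neither.

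**The plan's own figures**
- Alpha: 0.05 − 0.00001 = 0.04999, which is 0.024995 in the non-inferiority direction.
- Power at 2% vs 2%, unconditional exact test on the score statistic: 85.1% at 283/282 and 84.9% at 284/281. This reproduces the SAP's 85%.

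**Bounds for the two claims together, one-sided**
- Sum: 2 × 0.024995 = 0.04999.
- If independent: 1 − (1 − 0.024995)² = 0.0494.

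**Simulation.** Each subject is a failure (≥ 50), a success (< 50) or has no data. Both tests are score tests at one-sided 0.024995, with 300,000 to 400,000 trials per scenario. For the primary, the score and exact tests gave the same power at 283/282. For the secondary, the score test stands in for the planned exact interval.

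*Both true differences at their margins.* Failures must differ by 4 points (6% vs 2%) and successes by 10. The other 6 points must therefore be extra no-data subjects on B/F/TAF. With 5% no data on control:

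| | ≥ 50 | < 50 | No data |
|---|---|---|---|
| B/F/TAF | 6% | 83% | 11% |
| DTG+F/TAF | 2% | 93% | 5% |

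| Control no-data rate | Primary falsely passes | Secondary falsely passes | At least one |
|---|---|---|---|
| 3% | 2.1–2.2% | 2.3% | 3.9–4.0% |
| 5% | 2.1% | 2.4% | 4.1% |
| 6% | 2.1% | 2.4% | 4.1% |
| 9% | 2.1% | 2.5% | 4.3% |

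*Slightly off that point* (5% no data on control):
- 7% vs 2% failures, successes 10 points apart: 2.7%.
- 6% vs 2% failures, successes 11 points apart: about 2.8%.

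*Equal no-data rates.* The difference in successes is then the difference in failures with its sign reversed. At 6% vs 2% only the primary claim can be false, and its chance is 2.1%. At 12% vs 2% both nulls hold, but the primary practically never passes; the chance of any false claim is 2.3–2.5%.

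**Discordance, which is not type I error** (primary fails, secondary concludes non-inferior; equal no-data rates)
- 2% vs 2%: about 14.5% at 5% no data (13–15% over 3–9%).
- 6% vs 2%: about 65% at 5% no data (74%, 61% and 53% at 3%, 6% and 9%).

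**With a fixed sequence.** If the primary null is true, any false claim requires a false primary pass, so the chance is at most 0.024995. If it is false, only the secondary claim can be wrong, again at most 0.024995. No alpha is split. A Bonferroni split would need 0.04999 / 2 = 0.024995 two-sided for each endpoint.

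**The case against.** The strongest reply is that there is only one confirmatory claim. The plan names one primary comparison and controls it. The only efficacy objective is tied to HIV-1 RNA ≥ 50 copies/mL, and the secondary objective is safety and tolerability. Protocol 8.5.2 introduces the < 50 endpoint as a summary. A reader might infer that the plan lets this endpoint rescue a failed primary. Neither document says so: the point rests on a formal rule that carries no condition, not on a statement that the primary is irrelevant. This limits the concern but does not remove it, because a stated conclusion at full alpha with its own margin is more than a summary.

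Three further objections stand.
- The discordance figures are not errors. At 6% vs 2% with equal no-data rates the true difference in successes is −4 points, inside the 10% margin, so the secondary conclusion is correct. At 2% vs 2% it is correct too, and the 14.5% mainly reflects the primary's 85% power.
- The contrast with superiority is weak. An upper bound below 0 is necessarily below 4%, so that condition is automatic for the interval rule. It does not show that the plan gates claims elsewhere and omitted a gate here.
- The ratio of the margins does not measure leniency. They apply to different endpoints, and the < 50 endpoint also counts no-data subjects as non-successes.

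**Conclusion.** The point holds in a limited form. Type I error for the primary claim is controlled at 0.04999 two-sided. Across the primary and key secondary claims it is not, because each carries the full level and no order is set.

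The inflation is moderate and local: about 3.9–4.3% one-sided against 2.5% nominal, with a ceiling of about 5%. It arises when B/F/TAF has both 4 points more failures and about 6 points more no-data subjects. It falls to about 2.7–2.8% slightly away from that point, and to at most about 2.5% when no-data rates are equal. These figures rest on the assumed no-data rates and the 283/282 split.

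A reader might take the 14.5% and 65% as error rates. They are not; they show how often the two conclusions would point in different directions, which is why the plan should say how to read that outcome.

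**What to change.** State in SAP 3.5 and 6.1.2.2.1 that the key secondary non-inferiority conclusion is drawn only if primary non-inferiority is shown on the FAS, and that otherwise its interval is descriptive. The alpha stays the same, in fixed sequence. Protocol 8.5.2 should be read in the same way.

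Timing limits what this achieves. SAP 2.2.1 reports that the Week 48 analysis has been conducted, and this SAP covers the final analysis. The rule should therefore be recorded in the SAP and the study report as an interpretive rule added after that analysis. It cannot be presented as prespecified error control.

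The cost is about one sentence in each place. Primary power is unaffected and nothing is lost if the primary was met. The downside is that no formal secondary conclusion is available if the primary failed.

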## 3.6. Missing Data and Outliers

## 3.6.1. Missing Data

A missing datum for a given study analysis window may be due to any of the following reasons:

- A visit occurring in the window but data were not collected or were unusable
- A visit not occurring in the window
- A subject prematurely discontinuing from the study before reaching the window

In general, values for missing data will not be imputed, unless methods for handling missing data are specified.

For missing last dosing date of study drug, imputation rules are described in Section 3.8.1. The handling of missing or incomplete dates for AE onset is described in Section 7.1.5.2, and for concomitant non-ARV medications in Section 7.4.2.

#### **3.6.2. Outliers**

Outliers will be identified during the data management and data analysis process, but no sensitivity analyses will be done to evaluate the impact of outliers on efficacy or safety outcomes, unless specified otherwise. All data will be included in the analyses.

## 3.7. Data Handling Conventions and Transformations

Laboratory data that are continuous in nature but are less than the lower limit of quantitation or above the upper limit of quantitation will be imputed as follows except for urine creatinine:

- A value that is 1 unit less than the limit of quantitation will be used for calculation of descriptive statistics if the datum is reported in the form of "< x" (where x is considered the limit of quantitation). For example, if the values are reported as < 50 and < 5.0, values of 49 and 4.9, respectively, will be used for calculation of summary statistics. An exception to this rule is any value reported as < 1 or < 0.1, etc. For values reported as < 1 or < 0.1, a value of 0.9 or 0.09, respectively, will be used for calculation of summary statistics.
- A value that is 1 unit above the limit of quantitation will be used for calculation of descriptive statistics if the datum is reported in the form of "> x" (where x is considered the limit of quantitation). Values with decimal points will follow the same logic as above.
- The limit of quantitation will be used for calculation of descriptive statistics if the datum is reported in the form of " $\leq$  x" or " $\geq$  x" (where x is considered the limit of quantitation).

Logarithmic (base 10) transformations will be applied to HIV-1 RNA and HBV DNA data for efficacy analyses. HIV-1 RNA results of 'No HIV-1 RNA detected' and "<20 copies/mL HIV-1 RNA Detected" will be imputed as 19 copies/mL for analysis purposes. HBV DNA results of "<20 IU/mL HBV DNA detected" or "No HBV DNA detected" will be imputed as 19 IU/mL for analysis purposes. HCV RNA results of "<15 IU/mL HCV RNA detected" or "No HCV RNA detected" will be imputed as 14 IU/mL for analysis purposes.

#### 3.8. Analysis Windows

#### 3.8.1. Definition of Study Day

**Study Day 1 for the Randomized Phase analysis** is defined as the day when the first dose of blinded randomized study drug (ie, B/F/TAF or Placebo, or DTG or Placebo, or F/TAF or Placebo) was taken, as recorded on the Study Drug Administration eCRF for "Randomized Phase"

**Last Dose Date for the Randomized Phase** analysis is the latest of the blinded randomized study drug (ie, B/F/TAF or Placebo, or DTG or Placebo, or F/TAF or Placebo) end dates recorded on the Study Drug Administration eCRF for "Randomized Phase".

If the last dose date for the randomized phase analysis is missing (eg, only year of last dose is known or completely missing due to lost to follow-up), the latest of the blinded study drug start dates and end dates, or the latest of clinical and the laboratory visit dates prior to the first dose date of B/F/TAF in the extension phase (if applicable), excluding the 30-day follow-up visit date, will be used to impute the last dose date. For other partial missing last dose date, please see the Appendix 7 for imputation rule details.

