# 6.4. Treatment Assessments (Week 4 - 48)

The following evaluations are to be completed at Weeks 4, 8, 12, 24, 36, and 48 unless otherwise specified.

Study visits are to be completed within  $\pm$  2 days of the protocol specified visit date (based on the Day 1 visit) through Week 12, and completed within  $\pm$  6 days of the protocol specified visit date through Week 36, unless otherwise specified. The visit window at Week 48 will be  $\pm$  6 weeks of the protocol specified visit date, and this clinical visit window coincides with the Week 48 statistical analysis window for HIV-1 RNA.

Regularly scheduled evaluations will be made on all subjects whether or not they continue to receive study drug.

- SF-36, HIV Symptoms Distress Module, WPAI and PSQI to be completed by the subject at Weeks 4, 12 and 48. Subject is to read questionnaire by himself/herself and write/mark answers directly onto questionnaires
- Review of AEs and changes in concomitant medications
- Complete physical examination (Weeks 24 and 48) (urogenital/anorectal exams will be performed at the discretion of the Investigator) or symptom-directed physical examination, as needed
- Vital signs measurement (blood pressure, pulse, respiration rate, and temperature), including weight
- Obtain blood and urine samples as described in Sections 6.10.1 and 6.10.2
- Document study drug dispensation and accountability for all study drugs dispensed.
- Subjects who meet the criteria for virologic failure will be managed according to the Management of Virologic Rebound Section 6.11.1 and 6.11.2

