#### 6.6. Post-treatment Assessments

## **6.6.1.** Early Study Drug Discontinuation Assessments

If the subject discontinues study drug prior to the End of Blinded Treatment Visit, the subject will be asked to return to the clinic within 72 hours of stopping study drug for the Early Study Drug Discontinuation Visit. Prior to the End of Blinded Treatment Visit, if a subject discontinues study dosing (for example, as a result of an AE), every attempt should be made to keep the subject in the study and continue to perform the required study-related follow-up and procedures through to the End of Blinded Treatment Visit (see Section 6.7, Criteria for Discontinuation of Study Treatment). If this is not possible or acceptable to the subject or investigator, the subject may be withdrawn from the study.

If the subject discontinues study drug during the OL extension, the subject will be asked to return to the clinic within 72 hours of stopping the study drug for the Early Study Drug Discontinuation Visit, and will be discontinued from both study drug and study.

At the Early Study Drug Discontinuation Visit, any evaluations showing abnormal results indicating that there is a possible or probable causal relationship with the study drug, will be repeated weekly (or as often as deemed prudent by the Investigator) until the abnormality is resolved, returns to baseline (Day 1) value, or is otherwise explained.

The following evaluations are to be completed at the Early Study Drug Discontinuation Visit:

- Review of AEs and changes in concomitant medications
- Complete physical examination (urogenital/anorectal exams will be performed at the discretion of the Investigator)
- Vital signs measurement (blood pressure, pulse, respiration rate, and temperature), including weight
- Obtain blood and urine samples as described in Sections 6.10.1 and 6.10.2
- Document study drug accountability for all study drugs dispensed

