- c. Based on the results of the genotypic and phenotypic assays, the subject will remain on study drugs or study drugs will be discontinued. If genotyping or phenotyping fails, a new ARV regimen may be configured at the discretion of the Investigator.
- d. If no new resistance is detected, HIV-1 RNA will be repeated (2-3 weeks later). Investigator reviews study drug continuation/discontinuation options and discusses with the Medical Monitor prior to study drug discontinuation
- e. A new ARV regimen will be configured, at the Investigator's discretion, and the subject will remain in the study.

# 6.11.2. Subjects with HIV-1 RNA ≥ 50 copies/mL at Study Drug Discontinuation, or Week 48

Subjects with HIV-1 RNA  $\geq$  50 copies/mL at study drug discontinuation, or last visit, or Week 48 will be considered virologic failures. Subjects with HIV-1 RNA  $\geq$  50 copies/mL at Week 48, will be asked to return for an unscheduled visit within the visit window for a retest.

Subjects with HIV-1 RNA  $\geq$  200 copies/mL at study drug discontinuation, last visit, or Week 48, will also have resistance testing conducted.

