## 6.1.1.2. US FDA-Defined Snapshot Algorithm

The analysis window at Week 48 is defined as from Study Day 295 to Study Day 378, inclusive. All HIV-1 RNA data collected on-treatment (ie, data collected up to 1 day after permanent discontinuation of study drug) will be used in the US FDA-defined snapshot algorithm. Virologic outcome will be defined as the following categories:

- **HIV-1 RNA < 50 copies/mL:** this includes subjects who have the last available on-treatment HIV-1 RNA < 50 copies/mL in the Week 48 analysis window
- HIV-1 RNA  $\geq$  50 copies/mL: this includes subjects
  - a) Who have the last available on-treatment HIV-1 RNA ≥ 50 copies/mL in the Week 48 analysis window, or
  - b) Who do not have on-treatment HIV-1 RNA data in the Week 48 analysis window and
    - 1) Who discontinue study drug prior to or in the Week 48 analysis window due to lack of efficacy, or
    - 2) Who discontinue study drug prior to or in the Week 48 analysis window due to AE or death and have the last available on-treatment HIV-1 RNA  $\geq$  50 copies/mL, or
    - 3) Who discontinue study drug prior to or in the Week 48 analysis window due to reasons other than AE, death, or lack of efficacy and have the last available on-treatment HIV-1 RNA ≥ 50 copies/mL.
- No Virologic Data in the Week 48 Window: this includes subjects who do not have on-treatment HIV-1 RNA data in the Week 48 analysis window because of the following:
  - a) Discontinuation of study drug prior to or in the Week 48 analysis window due to AE or death and the last available on-treatment HIV-1 RNA < 50 copies/mL, or
  - b) Discontinuation of study drug prior to or in the Week 48 analysis window due to reasons other than AE, death, or lack of efficacy and the last available on-treatment HIV-1 RNA < 50 copies/mL or,
  - c) Missing data during the window but on study drug.

The flowchart of the US FDA-defined snapshot algorithm is provided in Appendix 2.

The Week 48 virologic outcomes for the US FDA-defined snapshot algorithm will be listed.

For switch trials, the US FDA-defined snapshot algorithm classifies subjects who discontinue study drug due to AE or death and have the last available on-treatment HIV-1 RNA value  $\geq 50$  copies/mL in the "HIV-1 RNA  $\geq 50$  copies/mL" category. For treatment naïve study population, these subjects will be classified in the "No Virologic Data in the Week 48 Window" category.

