## Appendix 2. Flowchart of US FDA-defined Snapshot Algorithm (for Switch Trial)

The following flowchart for US FDA-defined snapshot algorithm is based on the US FDA Guidance on Human Immunodeficiency Virus-1 Infection: Developing Antiretroviral Drugs for treatment {U. S. Department of Health and Human Services 2015}.

\* On-Treatment HIV-1 RNA data include all HIV-1 RNA data for subjects who are on-going and HIV-1 RNA data up to 1 day after the last dose date of study drug for subjects who prematurely discontinue or complete study drug.

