## 11) Last Dose Date and Last Study Date

a) Last Dose Date (ie, TRTEDTC, TRTEDT, TR01EDT or TR01EDTC) in ADSL for randomized phase analysis and all B/F/TAF analysis was defined in SAP Section 3.8.1.

For subjects with a partial last dosing date (ie, month and year of last dose are known), the latest of the dispensing dates of study drug bottles, study drug start dates and end dates, and the imputed last dose date [day imputed as 15] will be used as the final imputed last dose date. However if dispensing date's month is after last dose date's month, data query is needed.

If subject died and the death date is complete (ie, not partial date) and before the imputed last dose date, the complete death date should be used as the imputed last dose date.

b) Last Study Date is the latest of the study drug start dates and end dates, the clinic visit dates, and the laboratory visit dates, including the 30-day follow-up visit date, for subjects who prematurely discontinued study or who completed study according to the Study Completion eCRF. If study drug start date or end date is partially missing (ie, only year and month are known), the day will be imputed as 15 for the purpose of this analysis.

If subject died and the death date is complete (ie, not partial date) and before the imputed last study date, the complete death date should be used as the imputed last study date.

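### The rule for a missing or year-only last dose date can place the last dose after true discontinuation, so off-drug HIV-1 RNA may count as on-treatment; few subjects are likely to be affected, and the error can go either way

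*SAP*

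**What the plan says.** SAP 3.8.1 (Definition of Study Day) covers a randomized-phase last dose date of which "only year of last dose is known or completely missing due to lost to follow-up". It is filled from blinded drug start and end dates or the latest clinic or laboratory visit before any open-label dose, "excluding the 30-day follow-up visit date, will be used to impute the last dose date". The rule for the all B/F/TAF analysis in the same section is parallel.

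If month and year are known, a different rule applies (SAP Appendix 8, item 11). It takes the latest of the dispensing dates, the drug start and end dates and a mid-month date: "the imputed last dose date [day imputed as 15] will be used as the final imputed last dose date". Visit dates play no part. Section 3.8.1 points to Appendix 7 for this rule, but Appendix 7 deals with COVID-19 visits.

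The snapshot in SAP 6.1.1.2 uses "data collected up to 1 day after permanent discontinuation of study drug". SAP Appendix 2 ties this to the last dose date: "HIV-1 RNA data up to 1 day after the last dose date of study drug for subjects who prematurely discontinue".

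The protocol continues follow-up off drug. Section 6.4 states: "Regularly scheduled evaluations will be made on all subjects whether or not they continue to receive study drug". Section 6.6.1 says "every attempt should be made to keep the subject in the study and continue to perform the required study-related follow-up". Under the virologic rebound schema (Figure 6-1, note e), "A new ARV regimen will be configured" and the subject stays in the study.

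**The concern.** The last visit is a reasonable stand-in for the last dose when a subject is lost to follow-up. It is a poor one for a subject who stopped drug, has no usable stop date and kept attending. The imputed last dose then becomes a late study visit, and every HIV-1 RNA up to that visit is treated as on-treatment.

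The exclusions in the rule do not reach this subject. Protocol 6.6.2 does not require the 30-day visit of someone who attends at least one visit after the discontinuation visit. Protocol 6.5.2 bars early stoppers from the open-label extension, so the cut-off at first open-label dose never applies to them. The only other limit is a complete death date (SAP Appendix 8, item 11). Nothing holds a year-only imputation within the known year.

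At stake is whether the Week 48 snapshot describes response on blinded study drug. The same date also feeds per-protocol membership (SAP 3.1.1.3), exposure and time to discontinuation (4.2.1), treatment-emergent adverse events (7.1.5.1) and laboratory abnormalities (7.2.2.1).

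**Working it through.** **1. Illustration (hypothetical subject).** Suppose a subject stops blinded drug on Day 84 for lack of efficacy, starts another regimen, and has HIV-1 RNA < 50 on Day 336, with the stop date missing. The Week 48 window is Day 295 to 378.
- True last dose: there is no on-treatment RNA in the window, so the lack-of-efficacy branch gives >= 50.
- Imputed last dose on or after Day 336: there is an on-treatment value in the window, so the result is < 50. The lack-of-efficacy branch is not reached, because it requires no on-treatment RNA in the window.
- The imputed date is at least 336 − 84 = 252 days late.

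**2. Which counts move** (subject with no true on-treatment RNA in the window):

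| Reason for stopping and last true on-treatment RNA | True category | Off-drug value in window | Scored as | Primary >= 50 count |
|---|---|---|---|---|
| Lack of efficacy, any value | >= 50 | < 50 | < 50 | falls by 1 |
| Other reason, >= 50 | >= 50 | < 50 | < 50 | falls by 1 |
| Other reason, < 50 | No virologic data | < 50 | < 50 | unchanged |
| Other reason, < 50 | No virologic data | >= 50 | >= 50 | rises by 1 |

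In the third row the < 50 secondary endpoint gains a responder and the subject wrongly enters the per-protocol set. A subject who does have a true on-treatment value in the window can also be misclassified if a later off-drug value in the window replaces it, in either direction.

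**3. Reproducing the plan's power figures.** Inputs from SAP 1.3, 1.4 and 6.1.1.4: 2% events in both arms, margin 4%, one-sided 0.025, 260 per arm planned, 565 actual, two-sided 0.04999 at analysis (one-sided 0.024995).
- Normal approximation: n = (1.960 + 1.282)² × 2 × 0.02 × 0.98 / 0.04² = 258 per arm, against 260 stated. Power at 260 per arm is 90.3%, against at least 90% stated.
- Unconditional exact test: order outcomes by the score statistic for a difference of 0.04, then take the largest tail probability over the unknown control rate. With 565 split as 283 and 282 (an assumption), power is 85.1%, against 85% stated.

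**4. Size of one event.** 1/283 = 0.35 percentage points. The planned 2% implies 0.02 × 282 = 5.6, about 6 control events. With 6 control events:

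| B/F/TAF events | Upper 95.001% bound | One-sided p | Margin met |
|---|---|---|---|
| 8 | 3.64% | 0.015 | yes |
| 9 | 4.10% | 0.028 | no |

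With 4 control events the change comes between 7 (p = 0.018) and 8 (p = 0.034).

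**5. Sensitivity, with assumed misclassification.** At true rates of 6% and 2% the chance of declaring non-inferiority is 2.1%. If 2%, 5%, 10% or 20% of true events in both arms were rescored as < 50, it becomes 2.4%, 2.8%, 3.7% or 6.3%. If this happened in the B/F/TAF arm only, it becomes 2.5%, 3.2%, 4.7% or 9.9%. At a 6% rate that arm has about 0.06 × 283 = 17 events, so the 20% case means 3 or 4 true failures with unusable stop dates. These shares are assumptions, and only the favourable direction is modelled.

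**The case against.** The strongest reply is that the subject described will hardly ever exist. Early stoppers are asked to attend within 72 hours (Protocol 6.6.1). Stopping for rebound is to be discussed beforehand with the Medical Monitor (6.11.1). Source records must hold drug start and end dates (9.1.5), and drug is accounted for at each visit (5.5). A subject who keeps attending but whose stop month is never established would be unusual. This stands, and it is why the point is minor.

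A reader might infer that off-drug suppression is generally credited as success in the primary endpoint. The documents do not support that. The primary endpoint counts >= 50, and a subject who stopped for another reason with a last on-treatment value < 50 is outside that count either way. Nor do they support a bias in one direction: off-drug viremia would be scored as an on-treatment failure.

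A reader might also take the 8-versus-9 boundary as evidence that the non-inferiority conclusion is at risk. It shows only that any single event can matter at the edge of an exact test. It says nothing about how often this rule produces one.

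Finally, the Week 48 primary analysis has already been conducted (SAP 2.2.1) and this SAP governs the final analysis. The text that governed the Week 48 derivation is not in the documents. An edit now cannot alter that decision; it affects later tables and safety windows.

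The gap itself survives: no text caps the imputed date at discontinuation.

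**Conclusion.** The concern holds as a minor defect in a date derivation. As written, SAP 3.8.1 misdates the last dose of a subject who stopped drug, stayed in the study and has a missing or year-only stop date. The main effects are on the < 50 secondary endpoint, per-protocol membership, exposure and the treatment-emergent windows. The primary count changes only in the situations set out in the working, and may rise or fall.

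The number of such subjects is not given and is probably very small. If 0 to 3 in an arm is assumed, the largest shift in that arm's primary percentage is 3 × 0.35, about 1.1 points, and only if every one of them changes the primary count in the same direction. The boundary figures rest on the assumed 283/282 split and on assumed event counts. The plan's stated power is unaffected.

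One reading is uncertain. The word joining the two date sources in the randomized-phase rule leaves their order unclear, and the parallel all B/F/TAF rule reads as the latest of all dates. The problem arises under that reading, or wherever visit dates are used.

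**What to change.** In SAP 3.8.1, in both the randomized-phase and all B/F/TAF rules, add that for subjects recorded as having prematurely discontinued study drug:
- the imputed last dose date may not be later than the earliest available of the recorded discontinuation date and the Early Study Drug Discontinuation Visit date;
- later visits and later bottle return dates are not used, since a late return would recreate the error;
- a year-only date is imputed within the known year.

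SAP 4.2.2 already uses a date of premature discontinuation to limit treatment duration for adherence, so such a date is expected to be available. The form that holds it should be named. Correct the cross-reference from Appendix 7 to Appendix 8, item 11. Then list every subject with a completely missing or year-only last dose date, and check whether any Week 48 snapshot category or per-protocol assignment would change.

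The cost is a few lines of text, one condition in the derivation and one listing. The downside is a slightly more complex rule for very few subjects.
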